## 4. HANDLING OF MISSING DATA

## 4.1 General Conventions

Dates will be presented in listings as DDMONYYYY. Listings will be presented as the collected or raw data with missing information presented as such: -- MONYYYY for missing day, DD - - - YYYY for missing month, and DDMON - - - for missing year. Missing day values will have the first day of that month imputed if calculating a start date, while stop dates will have the last day of that month. Missing month and/or year will require a review of patients with similar events. The month and/or year will be selected such that the mean value is approximated using that particular value(s).

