- A new anti-cancer treatment is started prior to documented progression and ≤ 30 days after treatment discontinuation, then censorship is at the date of the last tumor assessment that verified lack of disease progression prior to the new treatment
- Patients with documentation of progression or death after an unacceptably long interval (i.e., 2 or more consecutively missed or indeterminate/not evaluable assessments) since the last tumor assessment will be censored at the date of last tumor assessment documenting no progression

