## **3.6.1** Treatment-Emergent Adverse Events (TEAE)

Adverse events will be considered treatment-emergent if:

- The event occurs for the first time after the start of study treatment and on or before 30 days after final dose of study treatment and was not observed prior to start of treatment
- The event was observed prior to the start of treatment but increased in NCI CTCAE v4 grade during study treatment

The eCRF will capture TEAEs on the adverse event page, while those events occurring pre-treatment will be captured on medical history.

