## 5.3 Standards

The information presented in this section describes the standard displays/mocks and analysis to be performed. Standard table displays will include columns for treatment groups called: seribantumab+fulvestrant/exemestane (seri+BB), seribantumab+fulvestrant (seri+f), seribantumab+exemestane (seri+e), placebo+fulvestrant/exemestane (pla+BB), placebo+fulvestrant (pla+f), placebo+exemestane (pla+e), and Overall. The primary comparisons are based on seri+BB versus pla+BB.

Continuous variables, as deemed appropriate, will be summarized using the number of non-missing observations, mean, standard deviation, median, minimum and maximum values. Missing data values will be treated as missing in summarization. No imputation of missing data will be performed.

Categorical variables will be summarized using the number of non-missing observations, frequency and percentage out of the number of non-missing observations in each category. Percentages will be presented to one decimal place (e.g., xx.x). Percentages will not be presented when zero counts occur.

Enrolled will be defined as those patients signing informed consent and completing entry criteria.

All p-values will be presented as two-sided using a SAS format (pvalue5.3). Primary efficacy inferential analyses will be tested against a one-sided, alpha at 0.025 (i.e., two-sided 0.05) unless stated otherwise.

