#### 5.6.2 Adverse Events

Adverse events will be coded using the latest MedDRA dictionary at the time of coding. NCI CTCAE v4.0 will be used to grade severity. Frequencies and percentages will be reported by System Organ Class (SOC) and preferred term (PT). Patients with multiple events for a category will be counted once in the highest CTCAE classification. Summary tables will include treatment-emergent AEs, unless specified otherwise. Treatment-emergent adverse events (TEAEs) will be defined as patients based on the event onset date relative to first dose of study drug in the study. Missing onset date for an event will be considered as TEAE. Adverse events with a starting date 30 or more days after the last dose date are not considered TEAEs. Relatedness will be considered: Possibly, Probably, or Definitely related per case report form classification. If relatedness is missing the adverse event will be considered TEAE. The order of reporting the events in summary tables will be according to the following where applicable:

- SOC will be alphabetically reported
- Descending order of frequencies according to the number of patients in the seribantumab treatment group experiencing an adverse event
- PT will be alphabetically reported

The following tables will be reported:

- TEAE
  - Any TEAE by SOC
  - Any TEAE by SOC and PT\*
  - Any TEAE by PT
  - Any TEAE by PT by NCI CTCAE Grade
  - Any TEAE by PT by cycle

- Any TEAE by PT by NCI CTCAE Grade by cycle
- Related TEAE
  - Any TEAE by SOC and PT\*
  - Any TEAE by PT
  - Any TEAE by PT by NCI CTCAE Grade
- TEAE NCI CTCAE Grade 3 or higher
  - Any TEAE by SOC and PT
  - Any TEAE by PT
- Related TEAE NCI CTCAE Grade 3 or higher
  - Any TEAE by SOC and PT
  - Any TEAE by PT
- SAE TEAEs only
  - Any SAE by SOC and PT\*
  - Any SAE by PT
- TEAE Various
  - Any TEAE Resulting in Dose Reduction
  - Any TEAE Resulting in Treatment Discontinuation
  - Any TEAE Resulting in Death

In the AE preferred term summary tables, a patient having multiple events within a System Organ Class is counted only once for that SOC. Similarly, a patient having multiple events under a preferred term is counted only once for that PT. Listings will be provided for all adverse event data.

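### SAP 4.1 dates any start with a missing day to the first of the month, with no floor at first dose: some early adverse events lose treatment-emergent status, and a new therapy can be placed before the progression it followed

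*SAP*

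**What the plan says.** **Partial dates.** SAP 4.1 (General Conventions) has one rule for every start date that lacks a day: "Missing day values will have the first day of that month imputed if calculating a start date". A stop date without a day is moved to the month's end instead. Nothing there stops an imputed start from falling before first dose or before a documented progression. Where month or year is missing, the section asks for a review of patients with similar events and a choice that approximates a mean. It does not define similar, which mean, or who decides.

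**Treatment-emergent events.** SAP 3.6.1 requires that "The event occurs for the first time after the start of study treatment", up to 30 days after the final dose, or that an earlier event rose in grade on treatment. SAP 5.6.2 classifies events "based on the event onset date relative to first dose of study drug in the study" and excludes those starting 30 or more days after last dose. It adds: "Missing onset date for an event will be considered as TEAE". Whether a date with a month and year but no day counts as missing is not stated.

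**New therapy and PFS.** The protocol synopsis (statistical considerations) censors any patient who starts new anti-cancer therapy before documented progression, at the last assessment before that therapy. SAP 3.1 lists two exceptions for patients who stop treatment without documented progression or death. One counts progression or death within 30 days of stopping as an event. The other applies where "A new anti-cancer treatment is started prior to documented progression" within the same 30 days, and censors. Table 3.1 counts progression on, before or within 30 days after discontinuation as an event. No order of precedence is given.

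**The concern.** Suppose first dose is on 10 March and an adverse event is recorded only as March. The rule dates it 1 March, before dosing, and it drops out of the TEAE tables unless its grade later rose. Had the whole date been missing, SAP 5.6.2 would have kept it. On that reading, a partly known date loses an event that an unknown date retains. At stake is the count of early treatment-emergent events, including those soon after the first infusion.

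For PFS, date order decides whether a progression is an event or is censored at an earlier scan. Scans are scheduled every 8 weeks, so the previous one is about 8 weeks earlier. New therapies are collected at contacts every two months, by telephone or visit (Protocol 6.6), so partial dates there are plausible. Censoring a patient because of a therapy begun after progression would be informative.

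The rule for a missing month or year cannot be reproduced by two programmers working independently, and it can decide either question.

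**Working it through.** **Inputs.** The day-1 rule (SAP 4.1); 28-day cycles (Protocol 3.1); the 30-day TEAE window (SAP 5.6.2); 58 PFS events for hazard ratio 0.57, one-sided 0.10, 80% power, 1:1 (Protocol 10.2). Assumptions: first-dose, last-dose and progression dates spread evenly over a 365-day year, and onset uniform within each interval stated. The plan gives no figure for partial dates.

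**The plan's event count.** By Schoenfeld's formula, events = 4 × (1.2816 + 0.8416)² / (ln 0.57)² = 18.03 / 0.3160 = 57.1, rounded up to 58. Power at 58 events is 80.5%. The protocol figure is reproduced; it is the count that new-therapy reversals would draw on.

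**Step 1: early adverse events.** Take a month of L days, first dose on day d, onset k days later. The imputed date precedes first dose only if d ≥ 2 and d + k ≤ L, that is for L − k − 1 first-dose days. Summed over twelve months this is 365 − 12(k + 1) = 353 − 12k days out of 365 (k up to 27). Averaging over k:

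- onset over all of cycle 1 (mean k = 13.5): (353 − 162)/365 = 191/365 = 52.3%
- first 14 days (mean k = 6.5): 275/365 = 75.3%
- first 7 days (mean k = 3): 317/365 = 86.8%

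In a 31-day month the cycle 1 share is 0% for first dose on day 1, 28/28 = 100% on day 2, 17/28 = 61% on day 15 and 4/28 = 14% on day 28. The remaining events fall in a later month and stay treatment-emergent.

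**Step 2: end of the window.** For a true onset 30 + j days after last dose (j = 0 to 30), the imputed date falls inside 30 days when the onset's day of the month is at least j + 2. That is again L − j − 1 days per month, not below zero. The sum is 28 × 191 + 18 + 7 + 0 = 5,373 out of 31 × 365 = 11,315, or 47.5%. These events are added to the TEAE count.

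**Step 3: new therapy after progression.** For a therapy started g days after the progression scan, the condition is the same:

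- 7 days: 269/365 = 73.7%
- 14 days: 185/365 = 50.7%
- 21 days: 101/365 = 27.7%
- 28 days: 18/365 = 4.9% (February contributes zero)

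**Step 4: when a reversal changes the endpoint.** Under the protocol synopsis any reversal turns the event into a censored time. Under SAP 3.1 it does so for patients who stop before progression and progress within 30 days. As illustration only: if 5% to 20% of progression events had a day-missing therapy start and 25% to 75% of those reversed, the events lost would run from 58 × 0.05 × 0.25 = 0.7 to 58 × 0.20 × 0.75 = 8.7. Power would be 80.1% to 75.5% if they were not replaced. Because the analysis is triggered by the event count, delay and informative censoring are likelier than lost power.

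**The case against.** **The eCRF may already separate these events.** SAP 3.6.1 puts TEAEs on the adverse event page and pre-treatment events on medical history. If the page decided status, nothing would be lost. But Protocol 7.2 and 9.2 collect adverse events from consent, so that page can hold pre-dose events and dates must separate them.

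**The missing-onset rule may cover partial dates.** It might. The text does not say so, and SAP 4.1 has a specific rule for a missing day. What stands is that an undercount follows from the literal rule; it has not been shown to occur.

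**The SAP protects most progressions.** This largely stands. A patient who stops at a progression scan and then starts therapy falls in the progression row of Table 3.1. Reversal needs the protocol wording, a patient who stopped before progression, or a program that compares dates only.

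**Partial dates may be rare.** Onset date is a required item (Protocol 9.2) and dosing visits come every two weeks. The documents give no frequency.

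A reader might also infer stronger points that the documents do not support:

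- *That nearly all such events are lost, since 29/30 = 97% of days in a 30-day month come after the 1st.* That is a share of first-dose days and presupposes onset in the same month. Even on that condition, with uniform onset, the share of events is 1 − 30/465 = 93.5%. Across cycle 1 it is 52%, and fully dated events are untouched.
- *That the error always understates harm.* Step 2 shows the opposite at the end of the window.
- *That SAP 5.3 contradicts the rule by stating "No imputation of missing data will be performed".* That sentence closes a paragraph on summarizing continuous variables; it does not address partial dates.

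**Conclusion.** The point holds as a defect in a stated rule. SAP 4.1 has no floor at first dose. Followed literally, it makes about half of day-missing cycle 1 events pre-treatment (52%, or 87% for week 1 onsets), given uniform onset and evenly spread first-dose dates. It also brings in about 47% of day-missing events that start 30 to 60 days after last dose. The PFS part is real but narrower: the chance of reversal falls from 74% at a 7-day gap to 5% at 28 days, and only some of the stated censoring rules let a reversal change the outcome. Total impact cannot be sized because the number of partial dates is unknown. The change is worth making because it costs almost nothing and removes a dependence on arbitrary dates.

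The SAP supplied names a different protocol number and a phase 3 design (SAP 1 and 1.2). The corrected rule belongs in whichever SAP governs this trial.

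**What to change.** Replace the start-date part of SAP 4.1 with fixed rules, before database lock:

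1. **Onset with day missing, in the month of first dose:** impute the first-dose date, unless the recorded stop date shows that the event ended before dosing. An imputed month-end stop date should not be used for this. State that onset on the first-dose date counts as treatment-emergent. No post-dose event is then dated before dosing (52.3% falls to 0%). Some true pre-dose events will be counted, the same direction as the existing missing-onset rule.
2. **Onset with month or year unknown:** count as a TEAE unless other data show that it was pre-treatment. State in SAP 5.6.2 how partial dates are treated.
3. **New-therapy start:** an imputed date alone must not override a documented progression in the same month. This choice favours counting an event, even where therapy truly came first, so add a sensitivity analysis with the opposite ordering. State the precedence between the protocol synopsis, SAP 3.1 and Table 3.1.
4. **Missing month or year in general:** delete the rule based on approximating a mean and rely on the rules above.

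The cost is one SAP paragraph, routine programming and one extra PFS run. No new data are needed. Report the number of partial dates by arm so that the impact can be seen.

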## 4.2 Tumor Assessments

Inadequate tumor assessment does not allow for a RECIST response determination and will be designated as Not Evaluable target response evaluation. An inadequate assessment will be defined as those with at least 1 missing measurement or non-measurable target lesion or baseline tumor assessments outside the screening evaluation window (i.e., after first dose date and prior to -28 days from first dose date). If a target lesion is too small to measure and does not have unequivocal complete disappearance, a default of 5mm will be assigned.

Different imaging of lesions should not be performed. Those tumor assessments that do not vary based on different imaging will be allowed. However, imaging variations that result in PR or CR based on the inconsistency of imaging will be reviewed carefully and may result in confirmation of that result at the following visit.

If non-target disease is not assessed and a patient is considered for a CR target response the overall disease response will be PR.

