#### Target disease

- Complete Response (CR): Complete disappearance of all target lesions with the exception of nodal disease. All target nodes must decrease to normal size (short axis < 10 mm). All target lesions must be assessed.
- Partial Response (PR): Greater than or equal to 30% decrease under baseline of the sum of diameters of all target measurable lesions. The short diameter is used in the sum for target nodes, while the longest diameter is used in the sum for all other target lesions. All target lesions must be assessed.
- Stable: Does not qualify for CR, PR or Progression. All target lesions must be assessed. Stable can follow PR only in the rare case that the sum increases by less than 20% from the nadir, but enough that a previously documented 30% decrease no longer holds.
- Documented Progression Disease (PD): 20% increase in the sum of diameters of target measurable lesions above the smallest sum observed (over baseline if no decrease in the sum is observed during therapy), with a minimum absolute increase of 5 mm.
- Not Evaluable: Progression has not been documented, and
  - $\circ$  one or more measurable target lesions have not been assessed
  - o or assessment methods used were inconsistent with those used at baseline
  - or one or more target lesions cannot be measured accurately (e.g., poorly visible unless due to being too small to measure)
  - o or one or more target lesions were excised or irradiated and have not reappeared or increased

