## Table 1. Objective Response Status at each Evaluation

Target Lesions	Non-target Lesions	New Lesions	Objective Status
CR	CR	No	CR
CR	Non-CR/Non-PD	No	PR
CR	NE, or Missing	No	PR
PR	Non-CR/Non-PD, NE, or Missing	No	PR
SD	Non-CR/Non-PD, NE, or Missing	No	SD
NE or Missing	Non-PD	No	NE
PD	Any	Yes or No	PD
Any	PD	Yes or No	PD
Any	Any	Yes	PD

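### SAP 4.2 calls the target response Not Evaluable whenever one target lesion is unmeasured, but the SAP appendix calls the same scan PD if the measured lesions already show progression; the SAP does not say which rule governs

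*SAP*

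**What the plan says.** **SAP 4.2 (Tumor Assessments, under Handling of Missing Data).** The definition is "An inadequate assessment will be defined as those with at least 1 missing measurement or non-measurable target lesion". A separate limb covers baseline scans outside the screening window. The consequence is: "Inadequate tumor assessment does not allow for a RECIST response determination and will be designated as Not Evaluable target response evaluation". The only relief is for very small lesions: "If a target lesion is too small to measure and does not have unequivocal complete disappearance, a default of 5mm will be assigned". Nothing is said about a scan on which the measured lesions already show progression.

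**SAP appendix (Objective Response Status at Each Evaluation, Target disease).** The Not Evaluable category opens with a precondition, "Not Evaluable: Progression has not been documented, and", and only then lists its reasons, among them "one or more measurable target lesions have not been assessed". PD is a "20% increase in the sum of diameters of target measurable lesions above the smallest sum observed", with an absolute increase of at least 5 mm. CR, PR and stable disease each carry a requirement that all target lesions be assessed; for stable disease it reads "Does not qualify for CR, PR or Progression. All target lesions must be assessed". PD carries no such requirement.

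**SAP appendix, Table 1.** Target PD gives overall PD whatever else is found. New lesions and non-target PD also give overall PD whatever the target status. A Not Evaluable target response with neither of these falls in the row "NE or Missing Non-PD No NE".

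**Link to PFS (SAP 3.1 and Table 3.1).** Events are death or documented RECIST v1.1 progression, using assessments made by the investigator. Patients without an event are censored at the last assessment whose overall response was something other than Not Evaluable. Section 3.3 applies the same censoring rules to PFS by independent review.

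**The concern.** The two parts of the SAP classify the same scan differently, and the scan concerned is one that shows progression. Under the appendix, PD takes precedence over Not Evaluable. Under 4.2, a missing measurement removes the target response before progression is considered. Neither part refers to the other and no precedence is stated, so the outcome depends on which section is programmed.

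What is at stake is the primary endpoint. If 4.2 is followed, the scan is not an event. The patient is then either counted later, if a further scan documents PD in time, or censored at an earlier progression-free scan. Censoring prompted by a scan that itself shows progression is related to outcome, which the log-rank test assumes censoring is not. A Not Evaluable scan also counts as one of the two consecutive missed or non-evaluable assessments after which SAP 3.1 censors a later PD or death.

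**Working it through.** **1. The plan's own figure.** Inputs from protocol 10.2: HR 0.57, one-sided alpha 0.10, power 80%, 1:1 allocation. Schoenfeld's formula gives

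d = 4 (z₀.₉₀ + z₀.₈₀)² / (ln 0.57)² = 4 (1.2816 + 0.8416)² / 0.3160 = 57.1, rounded up to 58.

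This reproduces the stated 58 events. Power at 58 events is Φ(0.5621 × √58 / 2 − 1.2816) = Φ(0.859) = 80.5%.

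**2. One scan under both rules.** The lesion sizes are assumed for illustration. The nadir at week 8 is 30 + 20 + 10 = 60 mm. At week 16 the first two lesions measure 55 and 30 mm and the third is not measured. There is no new lesion and non-target disease is not PD.

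- Measured sum: 55 + 30 = 85 mm.
- Thresholds: 1.2 × 60 = 72 mm and 60 + 5 = 65 mm. Both are exceeded; the increase is 25 mm, or 25/60 = 42%.
- The unmeasured lesion cannot have a negative diameter, so the full sum is at least 85 mm.

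| Step | Appendix | SAP 4.2 |
|---|---|---|
| Is the scan adequate? | Not asked for PD | No, one measurement is missing |
| Target response | PD | Not Evaluable |
| Overall response (Table 1) | PD | Not Evaluable |
| PFS at week 16 | Event | No event |

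The appendix does not spell out comparing a partial sum with the full nadir sum. It follows from the precondition on Not Evaluable and from the absence of an all-lesions requirement for PD.

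**3. What happens next if 4.2 is followed.** Three routes are open under SAP 3.1 and Table 3.1.

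- Treatment continues and the next complete scan shows PD: the event is counted, later.
- Treatment stops and PD is documented within 30 days: the event is counted, later.
- Treatment stops without PD documented in that window, or new therapy starts first: the patient is censored at the last progression-free scan, here week 8.

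**4. Size.** The documents give no rate of incomplete scans. Assume that a share *a* of PD scans has an unmeasured target lesion, and that in a share *b* of those PD rests on the measured target lesions alone. Events affected = 58 × a × b. The power column takes the worst case, in which every affected event is lost and not replaced.

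| a | b | Events affected | Events left | Power |
|---|---|---|---|---|
| 0.02 | 0.30 | 0.35 | 57.65 | 80.3% |
| 0.05 | 0.40 | 1.16 | 56.84 | 79.9% |
| 0.10 | 0.60 | 3.48 | 54.52 | 78.6% |

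If the analysis instead waits for 58 counted events, as the protocol synopsis implies, the true events needed are 58 / (1 − ab). That is 58 / 0.994 = 58.4 to 58 / 0.94 = 61.7. Out of 80 patients this is 73% to 77%, against 58/80 = 72.5% planned.

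The 58 comes from the protocol. The SAP text describes a different design (phase 3, 2:1, 195 events), so these figures apply its scan rule to this trial's event target.

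**The case against.** The strongest objection is that the primary endpoint is investigator-assessed. SAP 3.1 takes the assessments as the investigator's own, and nothing states that response will be recomputed from lesion measurements to overrule a recorded PD. If the investigator records PD and that record is used, the event counts and 4.2 does no harm to the primary analysis. This stands as a limit: the effect is conditional. It does not remove the conflict, because 4.2 says such scans will be designated Not Evaluable and does not exempt investigator calls.

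A second objection is that the appendix is the detailed algorithm and should govern. That reading is sensible, but nothing in the SAP compels it, and 4.2 is where a programmer would look for missing-data rules.

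Third, the event is often delayed rather than lost. Protocol 7.7 continues scans every 8 weeks until investigator-assessed PD, protocol 4.4 asks for a scan at discontinuation, and one Not Evaluable scan does not trigger the two-scan rule. This also stands. Recovery has limits: the further scan in protocol 4.4, 8 weeks after termination, falls outside the SAP's 30-day window, and scheduled scans stop once the investigator calls PD.

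Fourth, the reach is narrow. Table 1 already protects progression by new lesion or non-target disease, and lesions too small to measure are set to 5 mm. This stands in full.

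A reader might infer something stronger: that the plan does turn real progressions into informative censoring and so biases the treatment comparison. The documents do not support that. They do not say 4.2 overrides the investigator, they give no frequency of such scans, and in a double-blind trial nothing in them indicates a direction of bias between arms.

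**Conclusion.** The inconsistency is real and confined to one kind of scan: at least one target lesion unmeasured, the measured target lesions alone at least 20% and 5 mm above the nadir sum, and no new lesion or non-target PD. For that scan SAP 4.2 with Table 1 gives Not Evaluable, and the appendix gives PD.

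It affects primary PFS only if 4.2 is programmed over the investigator's PD call. It affects the SAP's independent-review PFS if 4.2 is applied there. In either case the progression is missed at that scan and is then counted later or censored earlier.

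The size is small. Under the assumed rates (2 to 10% of PD scans incomplete, 30 to 60% of those resting on target lesions alone), about 0.3 to 3.5 of 58 events are affected. Power moves from 80.5% to between 80.3% and 78.6% if all of these are lost; with an event-triggered analysis the main result may be a later cut-off. The case for acting is that the same scan should not be an event or a non-event according to the section programmed, and the choice should be fixed before outcomes are known.

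**What to change.** In SAP 4.2, add wording to this effect:

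> A missing or unmeasurable target lesion makes the target response Not Evaluable only if progression is not already documented. If the sum of the measured target lesions alone is at least 20% and at least 5 mm above the nadir sum, the target response is PD on that scan date.

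This brings 4.2 into line with the appendix. New-lesion and non-target PD need no new text, because Table 1 already covers them.

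The cost is one sentence and one programming condition. No new data are needed and the 58-event target does not change. It should be done before database lock.
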